5 TREATMENT

5.1 Selection of the Phase I starting dose and schedule

5.1.1 Rationale for starting dose BI-1206 and rituximab

BI-1206 (single agent) will be given at a starting dose of 0.4 mg, please refer to Section 2.3.1 for rationale.

The BI-1206 dose levels are flat doses given in units of mg for each cohort, whereas the rituximab doses are adjusted for the body surface area (BSA) of each patient and given in units of mg/m².

The dose(s) of rituximab used in Part A & B of the study will be a fixed dose of 375 mg/m² based upon the approved dose of rituximab.

For the purpose of this trial, all patients including CLL will receive 375 mg/m² for every rituximab infusion for consistency. The proposed weekly dosing schedule with BI-1206 and rituximab is in line with the rituximab SmPC standard of care for patients who receive rituximab alone. The 8 weekly maintenance therapy schedule is at a frequency in line with rituximab administration post chemotherapy and will only be given if patients are showing clinical benefit as defined in Section 10.2.

Single agent BI-1206 (Arm 1) will be initiated first in Part A and BI-1206 in combination with rituximab (Arm 2) may start once the intrapatient dose escalation cohort (Cohort 1) in Arm 1 has been completed.

The starting dose level for BI-1206 in Part A, Arm 2 will not exceed the highest dose of BI-1206 that has been safely given as a single agent in Part A, Arm 1 and deemed safe to be given in combination, following review in the Dose Decision Meeting (see Section 5.3). This will allow assessment of any single agent BI-1206 toxicity at the specified dose level to decide if it would be clinically appropriate to start the combination arm (Part A, Arm 2)

Once the combination dose escalation arm (Arm 2) is opened, both arms will run in parallel but independently, to determine RP2D of single agent BI-1206 in Part A, Arm 1 and RP2D of BI-1206 in combination with rituximab in Part A, Arm 2 (see Sections 5.4 and 5.5).

The RP2D of BI-1206 in the relevant arm (single agent or combination) needs to be established in Part A before the respective expansion cohort in Part B of the trial opens to recruitment (single agent expansion cohort, Arm 1 and combination expansion cohort, Arm 2, see Sections 5.7 and 5.8). Arm 1 and Arm 2 in Part B may open and progress independently of each other.

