5.3 Communication Plan where dose escalation (Part A) is to occur

5.3.1 Organisation and preparation for dose decision meetings.

Dose decision meetings will be organised by the Sponsor for weekly review of patient data during the first three weeks of the intra-patient dose escalation cohort in Arm 1 only, and subsequently during or following Week 5 of the last patient recruited to each cohort in Arm 1 or in Arm 2. Dose decision meetings will be triggered and occur independently for each treatment arm.

Required attendees/functional groups are as defined in the Sponsor's SOP: Sponsor Pharmacovigilance (PV) representative, Sponsor Medical Sciences representative (MS), Sponsor Clinical Study Manager or appropriate delegate, CI and PIs with patients at their sites undergoing review (a nominated sub- or co-investigator may attend in the PI's place if necessary). Optional attendees are Research Nurses or other relevant site staff and the following Sponsor representatives; Clinical Research Associates (CRAs), Clinical Study Co-ordinator (CSC), Clinical Data Manager (CDM) and, Project Leader (PL). PI's who do not have patients in the cohort under review are encouraged to attend but not required.

Prior to the dose decision meeting, the Sponsor will distribute the agenda and all necessary data to the meeting attendees and all study PIs if they are not available to attend the meeting, specifying which patients and data will form part of the review. The essential data to be reviewed to make decisions concerning changes in dose will be defined in the monitoring guidelines for the study. These will consist primarily of clinical data listings from Data Management (DM), safety data listings from PV and available pharmacokinetic and pharmacodynamic (PK/PD) assay data.

For intra-patient dose escalation, in order to ensure that the most recent trial data is under review data listings will be reviewed alongside anonymised safety data signed off by the site Investigator and faxed or emailed from site directly.

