^a Assumes that no clinically relevant ≥Grade 2 related toxicity has occurred

^b Assumes that no DLTs are encountered and is also dependant on number of patients that need to be replaced (if patient withdraws for reasons other than DLT).

5.4.1 Action if DLT observed in Cohort 1 (0.4mg to 50 mg), Part A Arm 1

Cohort 1 will consist of a minimum of a single patient, with intra patient dose escalation permitted up to a maximum weekly dose of 50 mg. Safety data will be reviewed on a weekly basis prior to the next planned dose and a decision to dose-escalate will be made based on this data.

If a DLT is observed at or below a dose of 50 mg the cohort will be expanded to up to six patients at the dose level at which the DLT is first identified (the most recent dose prior to onset of the event identified as a DLT). If one out of the six patients experiences DLT, intra-patient dose escalation will cease but standard dose escalation will continue; subsequent cohorts will be expanded to three patients. If two or more out of the six patients experiences a DLT, decisions about future patients will be made in accordance with Figure 4.

5.4.2 Dose escalation and action if clinically relevant \geq Grade 2 related toxicity observed at dose levels from Cohort 2 onwards, Part A Arm 1

From Cohort 2 onwards, all cohorts will include a minimum of one patient (see Figure 4)

- In the first patient recruited, any episode of clinically relevant \geq Grade 2 related toxicity would trigger cohort expansion to a minimum of 3 patients.
- Clinical relevance of the related toxicity will be determined by review and agreement between the relevant Investigator, Chief Investigator and Sponsor according to the following definition:

[figure not shown]
The test of clinical relevance is that the adverse event in question would cause the Investigator to re-evaluate the risk-benefit assessment of continuing therapy for the patient experiencing the event and to conclude that on a balance of probabilities, the risk-benefit ratio could be materially worsening

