5.9.2 Management of infusion related reactions

Pre-medications as specified of oral paracetamol 1 gram and IV chlorphenamine 10 mg will be administered as standard at least 30 minutes prior to each BI-1206 or rituximab infusion. Hydrocortisone 100 mg IV or dexamethasone 8 mg IV may also be administered prior to administration of BI-1206 or rituximab infusion, at the same time as the chlorphenamine and paracetamol at the Investigator's discretion. Alternative premedication steroids, antihistamine and analgesics (painkillers) may be used if clinically indicated according to Investigator's judgement, after discussion and approval from the CI and Sponsor.

Patients should be carefully monitored for signs of CRS or acute infusion reaction during each infusion, e.g. signs such as urticaria, wheeze, hypotension, tachycardia, dyspnoea (shortness of breath), etc. This monitoring period will last up to at least 4 hours after the first BI-1206 infusion and at least 30 minutes after every subsequent BI-1206 infusion. For rituximab infusions, this monitoring period will last up to at least 30 minutes after the end of each infusion.

Should patients develop any of the symptoms described above despite pre-medication (with or without steroids), the infusion must be stopped immediately and IV hydrocortisone 100 mg or IV dexamethasone 8 mg administered. Alternative steroid treatment may be used if clinically indicated according to Investigator's judgement. Once the reaction has stopped, infusion of BI-1206 or rituximab may restart with a 50% reduction in the rate of infusion. If IV hydrocortisone/dexamethasone is

insufficient, the reaction may be further managed with antipyretics, anti-histamines, intra-venous sodium chloride (NaCl), bronchodilators and additional glucocorticoids as required and as per local protocols.

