7.2 Evaluations during Induction Therapy (Weeks 1-8)

- Symptom-directed physical examination: if clinically indicated, a symptom-directed physical examination is to be performed within 24 hours prior to each BI-1206 administration and at Week 5. Patients in **Cohort 1, Arm 1 only** will also attend for this assessment at 72 hours post infusion at Weeks 1 to 4 (on Days 4, 11, 18 and 25).
- WHO performance status, to be recorded within 24 hours prior to each dose of BI-1206 or rituximab and at Week 5. This will also be assessed for patients in Cohort 1, Arm 1 only, 72 hours post infusion at Weeks 1 to 4 (on Days 4, 11, 18 and 25) for dose escalation purposes. Temperature, pulse rate, seated BP, to be recorded within 2 hours prior to each dose of BI-1206 or rituximab and at Week 5. These will also be assessed for patients in Cohort 1 at Day 4 of Weeks 1 to 4 (Days 4, 11, 18 and 25) for dose escalation purposes.
- During the first BI-1206 infusion for each patient: Pulse rate, temperature and seated BP must be measured every 15 minutes for the first hour and then within every 30 minutes until the end of the infusion. Where the infusion lasts less than an hour these should be measured every 15 minutes.
- During second and subsequent BI-1206 infusions and all rituximab infusions for each patient: Pulse rate, temperature and seated BP must be measured within every 30 minutes until the end of the infusion.

- After the BI-1206 or rituximab infusions for each patient: Pulse rate, temperature and seated BP must be measured at 30 minutes (\pm 5 minutes) after the end of the infusion and, in Part A, Week 1 at 2 and 4 hours after the end of the BI-1206 infusion.

In Arm 2, where BI-1206 and rituximab are given on the same day, the pulse, temperature and seated BP should be measured within 2 hours prior to the BI-1206 infusion, at the end of the BI-1206 infusion, within every 30 minutes between the infusions prior to the start of the rituximab infusion and at the end of the rituximab infusion.

- **For patients receiving rituximab treatment:** Weight measured during screening should be used for BSA calculation for induction therapy.

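### In Cohort 1 the closest acute monitoring falls on 0.4 mg, because Sections 7.2 and 5.9.2 tie it to the first infusion and not to each higher dose

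*Combined protocol and SAP*

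**What the plan says.** Three monitoring rules in the protocol depend on infusion number or week.

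- **Post-infusion vital signs (7.2).** One set is due 30 minutes (±5) after each infusion. Further sets are due "in Part A, Week 1 at 2 and 4 hours after the end of the BI-1206 infusion".
- **In-infusion vital signs (7.2).** At the first BI-1206 infusion they are taken every 15 minutes for the first hour, or throughout if the infusion is shorter than an hour. "During second and subsequent BI-1206 infusions and all rituximab infusions for each patient", the spacing is within every 30 minutes.
- **Observation for infusion reactions (5.9.2).** It lasts "at least 4 hours after the first BI-1206 infusion and at least 30 minutes after every subsequent BI-1206 infusion".

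Section 5.4.1 describes Cohort 1 as "a minimum of a single patient, with intra patient dose escalation permitted up to a maximum weekly dose of 50 mg". Table 1 in Section 5.4 sets the weekly doses at 0.4, 2, 10 and 50 mg.

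Some procedures were adapted to this cohort. On vital signs, Section 7.2 adds: "These will also be assessed for patients in Cohort 1 at Day 4 of Weeks 1 to 4 (Days 4, 11, 18 and 25"). Section 5.3.1 provides for "weekly review of patient data during the first three weeks of the intra-patient dose escalation cohort in Arm 1 only", and Section 5.4.1 says: "Safety data will be reviewed on a weekly basis prior to the next planned dose and a decision to dose-escalate will be made". Section 8.3.1.1 requires a PK sample before, at the end of, and 4, 24, 48 and 72 h after every induction infusion in Cohort 1.

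**The concern.** In most of the trial, the first infusion is also the patient's first exposure to the assigned dose, so a first-infusion rule covers new dose levels. In Cohort 1 that holds only for 0.4 mg. The 2, 10 and 50 mg doses are each a patient's second, third or fourth infusion, and each is five times the one before. They fall under the lighter rules for later infusions although no human is known to have received them.

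Section 2.2.8 expects infusion reactions with BI-1206 and names blood pressure change as a theoretical effect, so pulse, temperature and blood pressure soon after a new dose are relevant safety data. Each step up in Cohort 1 rests on a review of what was recorded at the dose just given. Finishing the cohort also has a consequence for the other arm: under Section 5.1.1 the combination "may start once the intrapatient dose escalation cohort (Cohort 1) in Arm 1 has been completed".

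**Working it through.** No sample size or error rate is involved. The check lays the rules of Sections 7.2 and 5.9.2 over the Table 1 doses and counts. It assumes unsplit doses.

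| Week | Dose (mg) | Step | In-infusion spacing | Fixed post-infusion readings within 4 h | Minimum observation | Next fixed vital signs |
|---|---|---|---|---|---|---|
| 1 | 0.4 | – | 15 min | 0.5, 2 and 4 h (3) | 4 h | Day 4 |
| 2 | 2 | 2/0.4 = 5-fold | 30 min | 0.5 h (1) | 30 min | Day 11 |
| 3 | 10 | 10/2 = 5-fold | 30 min | 0.5 h (1) | 30 min | Day 18 |
| 4 | 50 | 50/10 = 5-fold | 30 min | 0.5 h (1) | 30 min | Day 25 |

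**Does another section close the gap?** Section 6.2.5.6 refers back to 5.9.2. The schedule in Section 7.6 lists vital signs by day and adds no 2 h or 4 h reading in Weeks 2 to 4. Section 8.3.1.1 requires a 4 h blood sample but attaches no vital signs to it.

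**Is the gap confined to Cohort 1?** Yes. From 100 mg upwards, each new Arm 1 level is first given in a patient's own Week 1, where the fuller schedule applies. The Arm 2 escalation patients also have the 2 h and 4 h readings in Week 1.

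**Which decisions follow a lightly monitored dose?** Four decisions follow Cohort 1 doses: 0.4 to 2, 2 to 10, 10 to 50, and 50 mg to Cohort 2 at 100 mg. The last three follow a dose with one fixed post-infusion reading.

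**Sets added if the Week 1 schedule applied at 2, 10 and 50 mg:**

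- Post-infusion: 3 doses × 2 readings = 6.
- In-infusion at 2 and 10 mg (30-minute infusions, Section 6.2.5.2): 2 readings against 1, so +1 each.
- In-infusion at 50 mg (starting at 50 mg/hr, Section 6.2.5.3, so at most 60 minutes): 4 readings against 2, so up to +2.
- In-infusion total: 1 + 1 + 2 = up to 4.
- All sets on the three infusion days now: 3 pre-dose + (1 + 1 + 2) in-infusion + 3 post-infusion = up to 10.
- After the change: 3 + (2 + 2 + 4) + 9 = up to 20.

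**The case against.** The strongest reply is that the change may reach nobody. Section 2.2.8 cites clinical data already reported from this trial, and Cohort 1 needs only one patient, so it is probably finished. That stands as a limit on the value of the fix. The documents do not say that the cohort is complete.

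The second reply is that a first-infusion rule is reasonable. Section 2.2.6 reports that rituximab reactions occur mainly at the first infusion, and Section 2.2.4.1 reports no cytokine release from whole blood in vitro. Premedication precedes every infusion, and all Cohort 1 doses are below the expected active dose. These points lower the risk. The rituximab experience, however, does not describe a dose that rises five-fold each week.

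Third, the effect on decisions is modest. The Cohort 1 expansion rule needs a DLT, Section 3.3 excludes Grade 3 infusion reactions from DLTs, and the Grade 2 expansion trigger starts at Cohort 2. A transient change at 2 h would have no rule-based consequence, though the weekly review could weigh it. Opening Arm 2 also needs its own dose decision.

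Some stronger readings are tempting but unsupported:

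- A reader might infer that the patient is unwatched from 30 minutes to 4 h, or until Day 4. The 30 minutes is a minimum, and PK draws bring staff contact at 4, 24 and 48 h. What is missing is scheduled readings.
- A reader might take the one-to-two-hour timing of rituximab reactions in Section 2.2.6 as proof that observation ends too early. That clock runs from the start of a long infusion. At the first-infusion rates in Section 6.2.11, 25 + 50 + 75 + 100 = 250 mg has been given by 2 h and the infusion may still be running. The timing does not transfer to a 30-minute infusion of 2 or 10 mg.
- A reader might express 10 and 50 mg as multiples of the preclinical reference dose. The rationale in Section 2.3.1 is largely blacked out and does not show whether the stated margin is a dose ratio.

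**Conclusion.** The point holds as an optional, low-cost improvement. The text shows a design choice, and a reader who inferred a contradiction between sections or a weakness in the later cohorts would go beyond it. Day 4 checks, PK sampling and weekly review were all fitted to escalation within the patient, whereas the acute vital-sign and observation rules were not.

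The size is three of four Cohort 1 dose levels, each with one fixed reading in the first 4 h where the 0.4 mg dose has three: 6 post-infusion sets per patient.

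The conclusion rests on two assumptions. One is that no other trial gave 2, 10 or 50 mg first; Section 2.2.5 calls this the first-in-human study and reports no earlier clinical experience. The other is that Cohort 1 is still open or that a replacement patient will be treated. If neither applies, the change has no practical effect.

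**What to change.** In Section 7.2, apply the 15-minute in-infusion readings and the 2 h and 4 h post-infusion readings to every Cohort 1 infusion at which the patient receives a higher dose than before, as well as to the first infusion. Extend the 4 h observation in Section 5.9.2 to the same infusions and carry the wording into Section 7.6. Take the 4 h reading with the 4 h PK sample that is already due.

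A replacement patient starting at 0.4, 2, 10 or 50 mg would then have the fuller schedule at 3, 2, 1 or 0 later infusions, and not at repeat 50 mg doses. This includes levels already given to someone else, because the rule follows the rise in dose for that patient.

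The cost is the up to 10 extra sets counted above for a patient who goes through all four doses, a few minutes of nursing time each. Because of the existing 4 h sample, the visit is at most slightly longer.

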7.3 Evaluations during maintenance therapy

For patients who demonstrate clinical benefit (as defined in Section 10.2) at Week 8 following their induction therapy, further treatment with BI-1206 (\pm rituximab) may continue. The patient will receive the same dose of BI-1206 \pm rituximab as they received during their induction therapy. Starting from Week 8 onwards (post scan results) maintenance therapy will continue every eight weeks (\pm 2 weeks) from the first maintenance dose for up to one year after the first dose of BI-1206 on the study.

- **Symptom-directed physical examination:** If clinically indicated, a symptom-directed physical examination will be performed prior to BI-1206 administration.
- WHO performance status to be recorded prior to BI-1206 or rituximab.
- **For patients receiving rituximab:** For maintenance treatment, weight should be measured prior to each dose and BSA recalculated if the patient's weight has changed by more than 10% from the weight used for the current BSA (i.e. weight at 1st maintenance will be compared to from weight measured at screening).
- Pulse rate, temperature and seated BP must be measured within 2 hours prior to each infusion, within every 30 minutes during the infusion and at 30 minutes (\pm 5 minutes) after the end of the infusion

Where BI-1206 and rituximab are given on the same day, the pulse, temperature and seated BP should be measured within 2 hours prior to the BI-1206 infusion at the end of the BI-1206 infusion, within every 30 minutes between the infusions, prior to the start of the rituximab infusion and at the end of the rituximab infusion.

- **Adverse events and concomitant treatments:** At each visit, before each BI-1206 administration, an assessment of any AE experienced since the previous visit must be made by the Investigator or Research Nurse and the start and stop dates of the AE together with the relationship of the event to treatment with BI-1206 and/or rituximab must be recorded in the medical records. All AEs must be graded according to NCI-CTCAE Version 4.02. Any concomitant treatment must also be recorded in the medical records and electronic case report form (eCRF).
- **Haematology, biochemistry and urinalysis:** must be repeated before each BI-1206 administration (and before each rituximab administration if given on a different day to BI-1206).
 - Haematology: See Section 7.1.3.
 - Biochemistry: See Section 7.1.3.
 - Urinalysis: See Section 7.1.3.
- **ECG:** performed if clinically indicated.
- **Eye exam:** performed if clinically indicated.

- Assessment of disease:

A CT scan will be performed every 16 weeks (\pm 2 weeks but must be performed and reported before the patient's BI-1206 infusion) and at off-study where a scan has not been performed in the previous 8 weeks.

Should the Investigator assess that the patient is no longer deriving clinical benefit (as defined in Section 10.2) from continued maintenance therapy, the patient will be withdrawn from the trial.

Patients with lymphomas: For patients who have [¹⁸F]FDG PET-avid disease at baseline whose CT scans show a complete response, an [¹⁸F]FDG-PET scan should be performed within 4 weeks of receipt of the CT scan results.

Patients with Waldenström's macroglobulinemia: a blood sample should be taken for assessment of serum paraprotein. Normal serum IgM levels should also be measured.

- Bone marrow aspirate:

- **CLL Patients:** Those patients who had positive test at baseline and who show a complete response for the first time at a disease assessment during the maintenance period will have a bone marrow sample taken. [REDACTED]

[REDACTED]

- **Patients with lymphomas:** Only those patients who had positive test at baseline and who show a complete response for the first time at a disease assessment during the maintenance period will have a bone marrow sample taken. [REDACTED]

[REDACTED]

- Pharmacodynamic blood sample for assessment of anti-drug antibody levels, should be taken as described in Section 8.3.
- Blood samples for PK analysis, will be taken at each of the time points specified in Section 8.3.

7.4 Evaluations at 'off-study' visit

The off-study visit will occur when a patient will no longer continue on the treatment portion of the trial (either induction or maintenance treatment). This may be because of any of the reasons outlined in Section 11 or for patients who have completed a year of maintenance therapy. If a patient comes off-study following the Week 8 assessments and prior to commencing maintenance therapy the Week 8 assessments will be considered the "off-study" assessments. At this visit the following investigations where possible will be performed:

- A symptom-directed physical examination including WHO performance status, temperature, pulse rate and seated BP.
- Haematology (see Section 7.1.3).
- Biochemistry (see Section 7.1.3).
- Urinalysis (see Section 7.1.3).
- Serum Immunoglobulins – IgA, IgM & IgG levels will be assessed.
- Beta-2-microglobulin.
- Eye examination as described in Section 7.1.3 within \pm 2 weeks of the off-study visit date.
- ECG: performed if clinically indicated.

- Assessment of disease (unless disease progression has been noted at an earlier assessment or, if the patient has gone on to maintenance therapy and an assessment has been performed within the previous eight weeks (56 days)):

CT scan to assess tumour burden within \pm 2 weeks of the off-study visit date;

- **Patients with lymphomas:** For patients who have FDG PET-avid disease at baseline whose CT scans show a complete response, an FDG-PET scan should be performed within \pm 2 weeks of the off-study visit date.
- **Patients with Waldenström's macroglobulinemia:** a blood sample should be taken for assessment of serum paraprotein.
- Bone marrow aspirate:
 - **CLL Patients:** Those patients who had positive test at baseline and who show a complete response for the first time at a disease assessment at the off-study visit will have a bone marrow sample taken. [REDACTED]
 - **Patients with lymphomas:** Only those patients who had positive test at baseline and who show a complete response for the first time at a disease assessment at the off-study visit will have a bone marrow sample taken. [REDACTED]
- Pharmacodynamic blood sample for assessment of ADA levels, should be taken as described in Section 8.3.
- Assessment of AEs.
- Review of concomitant treatments.

